4.4 Statistical Design and Power

General considerations

All statistical analyses will be estimated using Stata v15 or higher. Descriptive statistics for Aim 1 will be calculated using all available data, and tests of hypotheses for Aim 2 will be performed using intent-to-treat approaches that include all participants randomized to a treatment condition regardless of whether they complete the intervention or not. Following enrollment of the full sample, treatment group differences in baseline demographic and sleep related functioning variables will be tested. Any variables that emerge as being significantly different between the two treatment groups will be included as covariates in all tests of Aim 2. If more than 3 variables emerge as being significantly different between the treatment arms, the full set of demographic and sleep related functioning variables will be used to estimate a propensity score indicating likelihood of membership in We-PAP relative to information control (IC); this propensity score will be included as a covariate in all tests of Aim 2.

Given the pilot nature of the proposed study, significance tests of study hypotheses will be performed using one-sided tests with $\alpha = 0.10$. Research concerning statistical criteria for pilot testing of clinical trials¹¹⁰ suggest that these relaxed statistical criteria, with an emphasis on a priori defined confidence intervals, are appropriate because the primary purposes of the proposed study are to evaluate whether there is reasonable evidence that We-PAP outperforms IC and, if so, to use this initial evidence to plan for a larger scale RCT of We-PAP. We will use these criteria with the primary adherence outcomes as a go/no go threshold for proceeding to a larger scale RCT. Provided that We-PAP outperforms IC as hypothesized, we will continue to use these criteria in estimating the 90% CI of the between group difference to determine the necessary sample size for a subsequent RCT. Because of the well-known phenomenon of pilot trials generating larger effect sizes than follow-on RCTs, we will use the lower limit of the 90% CI to anticipate this reduction in effect size and conservatively plan for a larger study.

Sample Size Determination

Study sample size was primarily determined by power analyses of primary adherence outcomes (adherence outcomes in patient and patient and partner sleep quality). Adherence outcomes (% nights with CPAP used ≥ 4 hours and numbers of hours of CPAP use per night) are available only for the patient and tests of study hypotheses depend on the precision of estimates of group effects at the highest level of nesting (i.e., the individual). As such, power estimates for tests of treatment effects on these variables were generated for standard linear models rather than MLMs.

Power estimates were generated using descriptive statistics for behavioral and cognitive behavioral CPAP interventions vs. IC reported in Wozniak et al.¹¹¹. For % nights with CPAP usage ≥ 4 hours, We-PAP adherence was assumed to be 47% and IC adherence was assumed to be 28%. For total hours of CPAP usage per night, We-PAP usage was assumed to be 5.44 hours/night and IC usage was assumed to be 4 hours/night with a SD of 2.12 hours/night within each group. Power estimates based on these assumptions indicate that a sample size of 20 couples per group will provide power of .8 or higher to detect between group differences of $d = .68$ for average hours of CPAP usage and O.R. = 4.36. These required effect sizes are consistent with the medium to large differences in adherence outcomes between behavioral treatments for CPAP and IC reported in Wozniak et al., 2014¹¹¹. Power estimates for patient and partners' sleep [actigraphy and diary-assessed] were generated using descriptive statistics for behavioral and cognitive behavioral CPAP interventions vs. IC as reported in Wozniak et al.,¹¹¹ as well as in Buysse et al.,⁵⁸ and Sweetman et al¹¹². Assumptions for secondary outcomes were: sleep efficiency, We-PAP: $M = 82.2$, $SD = 1.16$, IC: $M = 79.99$, $SD = 1.15$; daytime sleepiness, We-PAP: $M = 4.9$, $SD = 0.3$, IC: $M = 5.2$, $SD = 0.45$. Power estimates for secondary outcomes were not available for differential treatment effects of CBT vs. IC for health-related quality of life, cognitive functioning, or relationship quality. Therefore, consistent with other psychosocial outcomes (e.g., depression, anxiety, etc.), differential treatment effects were assumed to be moderate to large, $d = .7$. The availability of these outcomes for both patients and partners permitted estimation of power for MLMs with adjustment made for assumed associations ($r = .3$) between relationship partners within a couple. Power estimates based on these assumptions indicate that a sample size of 20 couples per group will provide power of .8 or higher to detect between group differences of $d = .54$ for all outcomes, which is smaller than or equal to effect sizes for all outcomes described above.

A final consideration in the determination of the sample size for the proposed study was the necessary sample size for stable and precise estimates of treatment effects using multilevel modeling. Maas and Hox's (2005)¹¹³ canonical work on necessary sample sizes for group level effects in MLM determines that group sizes of 20 members and larger is sufficient for generating unbiased estimates. Given that primary questions center on treatment effects in the proposed study, 20 couples per treatment ensures an adequate sample size for generating unbiased estimates of treatment effects thus permitting use of MLM to test study hypotheses.

Analysis Plan

Aim 2

Both primary outcomes will be analyzed using a two-level MLMs as described by the following series of equations:

$$\text{Level-1: } Y(\text{Adherence})_{ij} = \beta_{0j} + e_{ij}$$

$$\text{Level-2: } \beta_{0j} = \pi_{0j} + \pi_{0[1 \text{ to } n]} * [\text{covariates determined by tests of between group differences at baseline in demographic and sleep variables}] + \pi_{0[n+1]} * [\text{Treatment}] + \mu_{0j}$$

where i represents daily measures total hours of CPAP use/whether total hours of CPAP ≥ 4 hours (0 = no, 1 = yes) over the 3 month follow-up and j represents individuals. Treatment is a dummy coded variable with 0 = IC and 1 = We-PAP. The level two intercept in this model, π_{0j} , represents the maximum likelihood estimate of average adherence and $\pi_{0[n+1]}$ provides a test of the primary study hypotheses. Separate models will be run for total hours of sleep and ≥ 4 hours of CPAP use as outcomes estimated using models with Gaussian and binomial distributions respectively.

Secondary outcomes will be analyzed using a three-level MLMs as described by the following series of equations:

$$\text{Level-1: } Y(\text{Outcome})_{ijk} = \beta_{0jk} + \beta_{1jk} * (\text{Pre vs. 3 month follow-up}) + e_{ijk}$$

$$\text{Level-2: } \beta_{0jk} = \pi_{00k} + \pi_{0[1 \text{ to } n]k} * [\text{covariates determined by tests of between group differences at baseline in demographic and sleep variables}] + \pi_{0[n+1]k} * (\text{Patient vs. partner}) + \mu_{0jk}$$

$$\beta_{1jk} = \pi_{1jk} + \pi_{1[n+1]k} * (\text{Patient vs. partner})$$

$$\text{Level-3: } \pi_{0jk} = \gamma_{000} + \gamma_{001} * [\text{Treatment}] + r_{00k}$$

$$\pi_{1jk} = \gamma_{100} + \gamma_{101} * [\text{Treatment}]$$

$$\pi_{1[n+1]k} = \gamma_{1[n+1]0} + \gamma_{1[n+1]1} * [\text{Treatment}]$$

where i represents repeated measurement of the outcome variable, j represents individuals, and k represents couples. Treatment is a dummy coded variable with 0 = IC and 1 = We-PAP; Pre vs. 3 month follow-up is a dummy coded variable with 0 = pre-treatment and 1 = 3 month follow-up; and, patient vs. partner is a dummy coded variable with 0 = patient and 1 = partner. The level three intercept in this model, π_{0jk} , represents the maximum likelihood estimate of average outcome, π_{1jk} provides a test of differential treatment effects, and $\pi_{1[n+1]k}$ provides a test of whether these effects differ for patients and partners. Separate models will be run for each outcome.

Missing Data. Mechanisms of missingness will be evaluated in outcomes and potential mediators with missing data. If missingness patterns are consistent with MAR assumptions, recently developed fully conditional specification with chained equations methods for multiple imputation of missing data in MLMs will be used to handle missing data^{114,115}. All variables in hypothesis tests plus additional auxiliary variables will be included; potential auxiliary variables will be carefully screened using methods recommended for small sample sizes¹⁰³. If missingness patterns are consistent with MNAR assumptions, we will consider the use of pattern mixture models¹⁰⁴ and conditionally dependent dropout¹¹⁶ models to minimize any potential bias in estimation of treatment effects.

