
Describe the project objectives and all the procedures that will be conducted for the proposed project (e.g. participant identification, data collection, data analysis, etc.): [HELP?](#)

Visit schedule: Baseline (pre-treatment), 1 month (questionnaires only), 3 months post PAP initiation. Participants will receive the 3 intervention sessions between baseline and 1 month.

Study design

Overall design: The overarching hypothesis of this study is that patients and partners who complete the couples based sleep health intervention (We-PAP) will have greater PAP adherence, improvements in sleep and quality of life compared to patients and partners with standard care plus information (IC). In this phase 2 trial, we will be adapting and testing the intervention modules then will conduct a 2-arm randomized controlled trial of the novel We-PAP intervention in comparison to IC.

Couples will be randomized in a 1:1 ratio using a randomization table created by the study statistician ([name]). Allocation will be concealed through using the online randomizer module in the RedCap data management system.

The study will be conducted over 20 months. The duration of participation for participants will be 3.5 months. Participants will complete a baseline assessment (pre-treatment), then 3 intervention sessions via telehealth. They will complete questionnaires at 1 month, then complete a final 3 months post treatment initiation assessment. This is a single site trial with multiple recruitment locations at the University of Utah Sleep Center and community clinics in the Salt Lake City area.

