medium sensitivity. The rest period will be calculated by blinded research staff using standardized procedures. The training protocol will ensure that scorers are within an acceptable agreement range before scoring study records. A random sample of 10% of records will be checked for quality control and retraining will be assigned if scoring is not within 90% of the values determined by the co-PI. Participants will be provided with verbal and written instructions as well as links to youtube.com videos with demonstrations. Participants will wear the Actiwatches for 7-10 days in order to maximize the possibility of collecting 7 nights. Data will be considered valid if there are at least 5 nights. After the watches are retrieved, research staff will use the Actiware software program to calculate the following variables: total sleep time, sleep onset time, sleep offset time, sleep duration, sleep efficiency, sleep latency, wake after sleep onset, and sleep fragmentation index. The Actiwatch will be administered with a sleep diary to assist in scoring the rest interval. Cognitive measures administered at baseline and 3-month follow-up include the Repeatable Battery for the Assessment of Neuropsychological Status (RBANS). We will also administer the cognitive difficulties scale to assess for selfreported cognitive problems. Other self-report questionnaires administered at baseline, 1-month and 3-months include: Self-efficacy for sleep apnea, functional outcomes of sleep questionnaire, the Couple Satisfaction Index, PAP tactics questionnaire, PROMIS sleep related impairment, Epworth Sleepiness Scale. Feasibility and acceptability measures: We will use a combination of quantitative and qualitative measures. Outcomes include percentage of participants completing intervention sessions, ratings of ease of participation in the telehealth, questions about the number and duration of sessions, perceived benefits of the intervention and enjoyment of the sessions. We will also ask open ended questions about the format, feedback on the content, materials and general feedback and suggestions for improving the interventions.

Measures

Screening: Potential patients and partners will complete screening measures over the phone or via a web link to verify inclusion/exclusion criteria including demographics, a medical history and medication use questionnaire and various measures for inclusion/exclusion criteria (e.g., sleep disturbance).

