Sleep: Objective sleep duration and sleep efficiency (as an indicator of sleep fragmentation) will be measured via wrist actigraphy (Actiwatch Spectrum, Phillips Respironics, Murrysville, PA). Self-reported sleep will be measured using a standardized sleep diary and the PROMIS sleep disturbance questionnaire.

PAP adherence will be recorded by the patient's PAP machine and remotely downloaded via the web. We will measure PAP adherence continuously. The main time point for adherence is at 3 months. We will record the average duration of use per night, % of nights with use >4 hours, and nights skipped.

Cognitive measures include the Repeatable Battery for Assessment of Neuropsychological Status (RBANS). This validated clinical tool assesses 5 domains

and has two versions (A and B) and will be used to assess cognitive function at baseline and 3-month follow-up⁹⁴. We will also administer the cognitive difficulties scale.

Other important self-report measures: Couples satisfaction index (4 item), quality of relationships inventory, items from the conflict subscale and the PAP tactics questionnaire (7 most common items will be administered), self-efficacy for sleep apnea, functional outcomes of sleep, PROMIS sleep related impairment, Epworth Sleepiness Scale, patient health questionnaire 8-item, cognitive failures questionnaire, 14-item.

Feasibility and acceptability measures: We will use a combination of quantitative and qualitative measures including intervention completion, patient satisfaction ratings and open-ended responses (attached in the documents section).

5. Characteristics of Participants/Inclusion Criteria:[HELP?](#)

Participant-entry criteria should be as detailed as necessary to define the participant population under study and, for clinical studies, to reduce confounding treatments or diseases. Precise criteria for age, gender, or another other factors (e.g. diagnoses, extremes in signs or symptoms, etc.) should be included.

Focus group inclusion:

Two focus groups will be patients and partners: Men and women who are partnered or married and share a bed ≥ 3 nights per week in which one of the couple has OSA. One focus group will be comprised of providers at the University of Utah Sleep Wake Center, able to read and write in English.

Field trial and RCT inclusion:

Patient and partner inclusion criteria: 1) Age ≥ 50 ; 2) Access to cellular (active data plan) or Wi-Fi, in order to complete the telehealth intervention.

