Patients inclusion criteria: 1) Diagnosed with OSA (AHI >10 or AHI >5 with impairment) and intend to start PAP treatment; 2) PAP naïve, re-starting PAP after failed compliance or low adherence (<4 hours per night) 3) Married or cohabiting with a romantic partner for >1 year; 4) Able to read/write English.

Partner inclusion criteria: 1) Able to read/write English. 2) Interested in improving their sleep,

Provider group criteria: Provider or staff at the University of Utah Sleep Center or affiliated clinics.

Mild Cognitive Impairment inclusion:

Referred from existing studies in [name] lab. Diagnosed with mild cognitive impairment, able to read and write in English, diagnosed with obstructive sleep apnea and tried positive pressure therapy for at least 1 week. Participants with mild cognitive impairment are experiencing the early stages of memory loss. They are independent in most or all of their daily activities and able to provide consent for this study.

6. Participant Exclusion Criteria:[HELP?](#)

Specific exclusion criteria should be listed which could interfere with the study design or place a participant at risk during the study. If no exclusion criteria, please state "None."

Focus groups exclusion criteria: none

Field trial and RCT exclusion criteria:

Patient only exclusion criteria: Concomitant OSA treatments (bariatric surgery planned in the next 3 months or bariatric surgery in the past year, ear nose and throat surgery for sleep apnea occurring in the 3 months before or planning for within the study period).

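### Covariates for both primary adherence models are chosen by chance baseline imbalance rather than by prognosis, which forgoes the precision that a covariate fixed in advance could give

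*SAP*

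**What the plan says.** SAP section 4.4, General considerations, provides that after enrolment is complete "treatment group differences in baseline demographic and sleep related functioning variables will be tested". The result decides the model: "Any variables that emerge as being significantly different between the two treatment groups will be included as covariates in all tests of Aim 2". If the count of significant variables exceeds three, a propensity score estimated from the whole candidate set enters as a covariate.

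The Analysis Plan for Aim 2 carries this into Level 2 of both primary models (nightly hours, and whether a night reached 4 hours). The covariate term there reads "covariates determined by tests of between group differences at baseline in demographic and sleep variables". The secondary models use the same term.

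The Protocol, under Study design, says: "Couples will be randomized in a 1:1 ratio using a randomization table". On how the primary result will be used, SAP section 4.4 says: "We will use these criteria with the primary adherence outcomes as a go/no go threshold for proceeding to a larger scale RCT".

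The available text fixes no covariate in advance, gives no level for the baseline tests and does not list the candidate variables. The one-sided 0.10 is stated only for the study hypotheses. Part of the SAP was not available, so the level and the list are treated below as assumptions, not as omissions.

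**The concern.** Under randomization, baseline differences between arms arise by chance. A significance test on them says nothing about what makes a covariate useful, which is its association with adherence. Under this rule a strongly prognostic variable is usually left out. A variable unrelated to adherence can enter by luck, where it costs precision.

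Precision matters here for two reasons. Planned power for hours has no slack above 0.80. The same result serves as the go/no-go criterion, and the lower limit of its 90% confidence interval is to size the next trial.

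**Working it through.** **Inputs.** From SAP Sample Size Determination: means of 5.44 and 4 hours per night, SD 2.12, 20 couples per arm. From SAP General considerations: one-sided alpha of 0.10. Power is worked at patient level on mean hours, as the SAP does. R² below means the share of between-patient variance in mean hours.

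**1. The plan's own figure.** d = (5.44 - 4)/2.12 = 0.679. Noncentrality = 0.679 × √(20/2) = 2.15. The noncentral t with 38 df gives power 0.800, so the stated 0.80 reproduces.

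**2. When a variable enters.** At two-sided 0.05 a given variable enters in 5% of trials, and at 0.10 in 10%. The entry threshold at 0.05 for a continuous variable is t(0.975, 38) × √(2/20) = 0.64 SD. With 12 independent candidates, the chance that at least one enters is 1 - 0.95^12 = 46%.

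**3. One covariate fixed in advance.** The variance of the treatment estimate relative to no adjustment is (1 - R²)(N - 3)/(N - 4). With N = 40 this equals 1 at R² = 1 - 36/37 = 0.027. Power, from the noncentral t with 37 df averaged over chance imbalance:

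| R² | 0 | 0.04 | 0.09 | 0.16 | 0.25 |
|---|---|---|---|---|---|
| Power | 0.79 | 0.80 | 0.82 | 0.84 | 0.87 |

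At R² 0.10 it is 0.823, about 2 points above no adjustment. Two covariates with R² 0 give 0.784.

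**4. The SAP rule, simulated.** Baseline t-tests at 0.05, all significant variables entered, propensity branch omitted. There were 12,000 trials per setting at correlations 0 and 0.3 (Monte Carlo error of the difference 0.2-0.4 points) and 8,000 at 0.6 and 0.8 (roughly 0.3-0.5 points). Change in power against no adjustment, in points, by number of candidates:

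| Correlation | Prognostic variables | 5 | 12 | 16 | 20 |
|---|---|---|---|---|---|
| 0 | one, R² 0.16 | -0.3 | -2.4 | -2.8 | -4.0 |
| 0.3 | one, R² 0.16 | -0.3 | -1.4 | -1.9 | -2.9 |
| 0.3 | half, joint R² 0.25 | +0.5 | 0.0 | -0.7 | -1.4 |
| 0.6 | one, R² 0.16 | +0.2 | -0.5 | -0.2 | not run |
| 0.6 | half, joint R² 0.25 | +1.0 | +1.2 | +1.0 | not run |
| 0.8 | one, R² 0.16 | +0.6 | +0.1 | +0.3 | not run |
| 0.8 | half, joint R² 0.25 | +1.3 | +1.5 | +1.7 | not run |

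At a 0.10 test level the correlation 0 and 0.3 settings range from +1.2 to -5.7. With a stabilised propensity score included, they range from +0.5 to -4.5 at 0.05; that branch fires in 0-5% of those trials.

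**5. Fixed covariate against the rule.**
- With one prognostic variable at R² 0.16, the fixed covariate gives 0.84. The rule's best case in the table is 0.80 + 0.006 = 0.81.
- With half of the candidates prognostic (joint R² 0.25, correlation 0.3), fixing one of them gives 0.82-0.84 against 0.79-0.81.
- At correlation 0.8 with 6 of 12 equally weighted, one such variable carries 0.25 × (1 + 5 × 0.8)/6 = 0.21 of the variance. The fixed-covariate power at R² 0.20 is 0.856, against 0.80 + 0.015 = 0.815 under the rule.
- With a single candidate of R² 0, the rule is slightly ahead (0.798 against 0.792), because it seldom adjusts.

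**6. Type I error.** With 12 to 20 candidates at 0.05, the rule gives 0.090-0.098 and the unadjusted test 0.097-0.101, against a nominal 0.10.

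**The case against.** The strongest defence is that the rule is laid down in advance, uses baseline data only and belongs to an exploratory pilot. All of that stands. A reader might infer that the rule biases the treatment effect or inflates type I error. Neither follows, and the simulated error is at or slightly below nominal.

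A reader might also infer that the rule always loses power against no adjustment. That depends on the candidates being many and weakly correlated, which the Protocol makes doubtful. Its actigraphy outputs ("total sleep time, sleep onset time, sleep offset time, sleep duration, sleep efficiency, sleep latency, wake after sleep onset, and sleep fragmentation index") come from the same nights and partly define one another. With four sleep questionnaires they would make 12 variables per person before demographics, if all count. At correlations of 0.6 to 0.8 the loss vanishes or becomes a small gain. This objection succeeds against the claim of harm relative to no adjustment. It does not rescue the rule against a fixed prognostic covariate.

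It is also tempting to cite the imbalance the rule leaves in place. Just under 0.64 SD, at R² 0.04 or 0.16, the shift is 0.640 × √R² × 2.12 = 0.27 or 0.54 hours. These are tail values. The mean absolute imbalance is about 0.25 SD, or 0.11 and 0.21 hours. The shifts go either way equally often and are already in the unadjusted standard error.

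Finally, the gain from a fixed covariate is conditional, because the documents give no R² for any baseline variable. A binary covariate at 50% prevalence needs a difference of 2.12 × √(0.027/0.25) = 0.7 hours per night to break even. It needs 2.12 × √(0.10/0.25) = 1.3 hours to reach R² 0.10. This stands, and it is why using no covariate must remain an option.

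**Conclusion.** The point holds as a matter of precision and is of minor to moderate weight. The rule selects by imbalance, so it forgoes most of the gain available from a covariate chosen for prognosis. Against no adjustment its effect on power for hours is roughly -4 to +2 points at a 0.05 test level. One fixed covariate costs 0.8 points if useless, gains about 2 points at R² 0.10 and about 7 at R² 0.25, and beat the rule in the settings with R² 0.16 or joint R² 0.25.

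The break-even of about 0.03 is against no adjustment. Against the rule it depends on the number of candidates. With ten independent ones the rule gives 0.778 even at R² 0, below the 0.792 of a fixed covariate.

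The 5% entry figure rests on an assumed 0.05 level. The number of candidates, their correlation and R² are also assumptions. Power for the 4-hour outcome was not computed, so nothing is claimed about its size there.

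**What to change.** Delete the baseline significance tests and the propensity-score rule. State that baseline characteristics are summarized by arm without tests. Before adherence is compared by arm, name one Level-2 covariate (at most two), justified as prognostic, and include it in both primary models regardless of balance. If none can be justified, state that none is used.

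Prior PAP status is one candidate. Eligibility already separates PAP-naïve patients from those "re-starting PAP after failed compliance or low adherence" (Protocol section 5), so no new data are needed. Its prognostic value is an inference, and it may not be among the variables the present rule tests.

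In the secondary models, drop the tested set or use a covariate defined for both partners, such as age ("Patient and partner inclusion criteria: 1) Age ≥ 50"). Prior PAP status is a patient-only criterion and should not be carried there. Little is lost by dropping covariates in those models, because they enter only the intercept while treatment is tested on the change from baseline.

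The cost is SAP wording, plus about 0.8 points of power for each covariate that proves non-prognostic (0.792 with one, 0.784 with two, against 0.800).

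### In the secondary-outcome model the imbalance covariates enter only the intercept equation, so they do not adjust the tested treatment-by-time effect for variables that predict change

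*SAP*

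**What the plan says.** SAP 4.4, General considerations, compares the arms at baseline on demographic and sleep-related variables and then states: "Any variables that emerge as being significantly different between the two treatment groups will be included as covariates in all tests of Aim 2". Should over three variables differ, one propensity score takes their place in the same tests.

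SAP 4.4, Analysis Plan, Aim 2, shows where the covariates go.

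- **Primary adherence model (two levels).** Covariates and Treatment stand in the same level-2 intercept equation, and that Treatment coefficient is the test.
- **Secondary-outcome model (three levels).** Covariates stand in the equation for β0jk, the level of the outcome. The equation for change has no covariate term: "\beta_{1jk} = \pi_{1jk} + \pi_{1[n+1]k} * (\text{Patient vs. partner". Treatment enters the change coefficient at level 3 as γ101.

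The text under the equations codes time as two waves (pre-treatment and 3 months) and says of the change coefficient that it "provides a test of differential treatment effects".

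**The concern.** The rule is meant to protect every Aim 2 test against chance imbalance. In the secondary model the covariate acts on the level at both waves, while the hypothesis is tested on the difference between waves. A term that adds the same amount at both waves drops out of that difference. A secondary result could then be reported as covariate-adjusted although the imbalance still acts on it in full.

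This is practical because the screened variables include sleep measures, and sleep is itself a secondary outcome. An imbalanced variable may therefore be the baseline value of an outcome under test, and such a value predicts change through regression to the mean.

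**Working it through.** **Inputs from the SAP.** 20 couples per arm; one-sided α = 0.10; secondary effect size from "detect between group differences of $d = .54$ for all outcomes"; "adjustment made for assumed associations ($r = .3$) between relationship partners within a couple"; "SD of 2.12 hours/night within each group" for the primary outcome.

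**Assumptions, not in the documents.** Imbalance Δ = 0.65 SD; slope δ of the covariate on change, 0.1 to 0.4; variance components .2 (couple), .3 (person) and .5 (residual), so that the outcome SD is 1; pre-post correlation .3 to .7; dropout 0 to 30%; true treatment effect 0.

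**1. The plan's own power figures.** Power = Φ(d√(n/2) − 1.282). For secondary outcomes the effective n per arm is 40/(1 + .3) = 30.8, so Φ(0.54 × √15.4 − 1.282) = 0.799. For hours of use, Φ(0.68 × √10 − 1.282) = 0.808 (0.801 with the noncentral t). Both agree with the stated .8 and do not bear on this point. They only set the scale.

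**2. Algebra.** As written, a person's outcome at time t (0 or 1) is

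Y_t = [level terms + b·x] + t·[γ100 + γ101·Treatment + role terms] + random terms.

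The change is Y_1 − Y_0 = γ100 + γ101·Treatment + role terms + error. The term b·x has cancelled. If the covariate truly shifts change by δ per SD, the arm difference in change is γ101 + δ·Δ, and δ·Δ stays in the estimate. A propensity score is also constant within person, so the same holds for it.

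**3. Size.** The smallest difference reaching two-sided p = .05 with 20 per arm is t(.975, 38 df) × √(2/20) = 0.640 SD, hence Δ = 0.65.

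| Slope δ | Bias δ × 0.65 | Share of d = .54 |
|---|---|---|
| 0.1 | 0.065 SD | 12% |
| 0.4 | 0.26 SD | 48% |

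With a standard error of 0.287, the one-sided false-positive rate when the imbalance favours We-PAP is 1 − Φ(1.282 − 0.065/0.287) = 15% at the low end and 1 − Φ(1.282 − 0.26/0.287) = 35% at the high end, against a nominal 10%.

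If the imbalanced variable is the outcome's own baseline value, the slope is −(1 − r). The bias is −(1 − r) × 0.65 = −0.195, −0.325 and −0.455 SD for r = .7, .5 and .3.

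**4. Simulation of the printed model.** 1,000 trials, complete data, δ = 0.4. Mean estimate of γ101, true value 0:

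| Imbalance | No covariate | As written | With covariate × time |
|---|---|---|---|
| Couple-level covariate | 0.260 | 0.260 | 0.000 |
| Person-level, both partners | 0.264 | 0.262 | −0.001 |
| Person-level, patients only | 0.317 | 0.219 | −0.011 |

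For a couple-level covariate the estimate is unchanged in every trial. For a person-level covariate the estimate averaged over patient and partner is likewise unchanged, but the patient coefficient can shift in a single trial (by 0.03 to 0.04 SD in absolute value in a REML check with 0 and 20% dropout).

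The third row moves because the printed model has no Treatment × role term at baseline. In a separate run with slope −0.3 and patients-only imbalance, the estimate went from −0.074 to −0.156, away from the true 0. Adding Treatment × role makes the shift exactly zero again, so this is leakage from an omitted term, not valid adjustment.

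**5. Dropout.** With 10 to 30% of couples lost and an imbalance shared by both partners, the covariate moves the estimate by 0.007 to 0.037 SD in mean absolute value, against standard errors of 0.24 to 0.34. The average bias is not reduced. Under the planned multiple imputation each completed dataset has both waves, so covariates can act only through the imputed values.

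**6. Primary model.** With the same imbalance and an assumed covariate-outcome correlation of .4, the unadjusted bias should be about 0.65 × .4 × 2.12 = 0.55 h/night. Simulation gives 0.56 unadjusted and 0.01 adjusted, so the rule works there.

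**The case against.** Several points on the other side stand.

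- **The rule is not void.** A reader might infer that the plan's protection against imbalance does nearly nothing. The documents do not support that. In the primary model it acts directly on the treatment effect, and the SAP ties the go/no-go threshold to the primary adherence outcomes.
- **The secondary model already handles part of the problem.** Baseline is a repeated measure with a free treatment difference, so stable differences in level are removed without any covariate.
- **The plan does not contradict itself.** It says that the variables will be included as covariates, and they are. It never promises covariate-by-time terms. The fault is that the inclusion has little effect on the tested quantity.
- **The bias is conditional.** Couples are randomised 1:1, so the unadjusted contrast is unbiased over randomisations. Harm needs an imbalance that occurs and a variable that predicts change. That every secondary outcome is biased does not follow.
- **The size is assumed.** A slope of 0.4 under these variances means a within-arm correlation with change of 0.4/√(1.0 + 0.16) = .37, which is strong for a generic demographic variable. The lower end of the range is as admissible as the upper.

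None of this answers the core point. A significant imbalance is exactly the situation for which the SAP wrote the rule, and there the secondary test is left essentially unadjusted.

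**Conclusion.** The point holds for the secondary outcomes only. With two waves, covariates placed only in the intercept equation leave treatment-by-time exactly unchanged for a couple-level covariate with complete data, and on average nearly unchanged for a person-level covariate imbalanced in both partners. When only patients are imbalanced the coefficient moves, but for the wrong reason, and the bias is not reliably removed.

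The cancellation needs no assumed effect sizes. The magnitude does: 0.065 to 0.26 SD for a 0.65 SD imbalance and slopes of 0.1 to 0.4, in proportion to their product. Only outcomes whose change depends on a variable that happens to be imbalanced are affected.

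It should be fixed before the secondary outcomes are analysed. Since the go/no-go decision rests on the primary model, it is not a fault that undermines the trial's main conclusion.

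**What to change.** In the three-level model, add covariate × (Pre vs. 3 month) terms, or propensity score × time, to the equation for β1jk for each secondary outcome. γ101 is then the covariate-adjusted difference in change. Where the imbalanced variable is the baseline value of the outcome being analysed, it is already the time-0 response. Modelling the 3-month value adjusted for baseline is the cleaner equivalent in that case.

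Cost: no new data, one degree of freedom per covariate, and a standard error about 3% larger (for example 0.287 to 0.297). The SAP's own switch to a propensity score above three variables limits the added terms to three. The primary model needs no change on this point.
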